# 1.2 Secondary Objectives

- To examine the efficacy of radiotherapy in improving quality of life for patients with advanced hidradenitis suppurativa
- To explore histologic changes following radiotherapy for advanced hidradenitis suppurativa
- To explore changes in ultrasound findings following radiotherapy for advanced hidradenitis suppurativa
- To determine possible changes in assessment of cutaneous discharge from HS lesions

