As reviewed in above case report, a center in Germany treated 231 HS patients over 20 years who failed other treatment options. These patients received multiple fraction schedules with multiple fraction sizes (0.5 Gy - 1.5 Gy per fraction up to a total dose of 3.0 Gy to 8.0 Gy in one series). Chronic

recurrences were treated with 2 or more series with a total dose of greater than 10.0 Gy. No acute side effects were observed in this study. Complete symptomatic relief was documented in 38% (89/231) patients by the end of therapy and 40% (92 / 231) of patients reported an overall improvement in symptomatology. Only two patients had no response.

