#### 3.1 Inclusion Criteria

- The subject must be diagnosed with HS at Montefiore HS Treatment Center, with Hurley Stage 2-3 (Recurrent abscesses or boils with diffuse or broad involvement, multiple interconnected sinus tracts in the whole area) [5]. See Appendix A for photos.
- Subject must have failed maximal medical therapy for HS or be ineligible for "standard" medical therapy or surgery
- Age > 20 years old
- Women of childbearing potential must:
  - Have a negative serum or urine pregnancy test within 72 hours prior to the start of study therapy
  - Agree to utilize an adequate method of contraception throughout treatment and for at least 4 weeks after study therapy is completed. Adequate methods of contraception include hormonal methods (i.e. birth control pills, patches, injections, vaginal ring, or implants), barrier methods (i.e. condom or diaphragm), intrauterine device, or abstinence.
  - Be advised of the importance of avoiding pregnancy during trial participation and the potential risks of an unintentional pregnancy
- All patients must sign study specific informed consent prior to study entry.

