# 4.2 Study Calendar

	Pre-treatment	Week 1	Week 5*	Week 9*	Week 13*	Week 25 & 49#
History and Physical Examination	Х	Х	Х	Х	Х	Х
Adverse Event Assessment	Х	Х	Х	Х	Х	Х
Questionnaires: DLQI, PROMIS	Х	Х	Х	Х	Х	Х
Photos	Х	Х	Х	Х	Х	Х
Ultrasound	Х		Х	Х	Х	Х
Blood Tests: CBC, CRP, ESR	Х	-	-	-	Х	Х
Serum or Urine Pregnancy Test	×	-	-	-	-	-
Skin Biopsy, Discharge Measurement	×	-	-	-	Х	Х
Radiotherapy	-	XXXXX	-	-	-	-

\*+/- 1 week

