# 4.3 Study Endpoints

The primary endpoint of this study is safety, defined as the absence of any treatment-related Grade ≥3 adverse events during radiotherapy or within 3 months of radiotherapy completion, scored using CTCAE version 4.0.[6] Secondary study endpoints include:

# Optional

- Quality of Life
  - Improvement in NIH Patient-Reported Outcomes Measurement Information System (PROMIS) measures, including pain interference and physical functioning at 3 months (and optionally at 6 months and 12 months) after treatment[7, 8]
    - A one point change, either positive (improvement) or negative (decline), will be considered to be clinically meaningful[9]
- Inflammation as measured by ultrasound.
  - Noninvasive imaging, such as ultrasound (US), allows for an objective assessment of subclinical disease activity.
  - Anechoic area will be measured in the dermis before and after treatment, as well as other sonographic criteria of HS [10](See Appendix for Sonographic Scoring and Diagnosis of HS)
  - As there are no validated ultrasound criteria to measure clinical improvement, reduction in anechoic areas and sonographic criteria will be calculated. It is estimated that the treatment will induce a 50% reduction in the anechoic area.
  - Anechoic areas and other sonographic criteria will be correlated with PROMIS scores and Hurley Staging.
- Evaluation of cutaneous discharge
  - Swabs will be collected from discharge and sent for fluid count, which will include evaluation of infiltrating leukocytes from the discharge.
- Immunohistochemical Evaluation of HS Tissue Biopsies
  - Tissue biopsies will be collected before and after treatment. Tissue sections will be evaluated by H&E as well as immunohistochemistry for infiltrating leukocytes and other cells, such as T cells, B cells, plasma cells, dendritic cells, macrophages, and keratin. Image J will be used to quantify cells in a standard manner for comparison before and after treatment.

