#### 5.0 STATISTICAL CONSIDERATIONS

A maximum of 20 patients will be enrolled into the study. The accrual rate is expected to be 1-2 patients per month based on the volume of patients with stage 2-3 HS treated within the Montefiore Hidradenitis Suppurativa Treatment Center. An early stopping rule for safety will be implemented as follows based on Simon's optimal two-stage design. After the first 6 patients have been enrolled, accrual will be temporarily suspended while these patients are monitored for occurrence of treatment-related grade ≥ 3 toxicity for 3 months. At the end of 3

months, results will be sent to the DSMB for further evaluation. The trial will be terminated early if more than 1 patient experiences grade  $\geq$  3 treatment related toxicity or any patient experiences grade 4 toxicity. Otherwise, upon approval from the DSMB, the second phase of recruiting will be initiated. If 1 or fewer grade  $\geq$  3 toxicities and 0 grade 4 toxicities are observed, the trial will continue until a total of 20 patients have been evaluated. At the end of the trial, the treatment will be considered safe and worthy of further study if no more than 3 patients experience grade  $\geq$  3 treatment related toxicity and none experience grade 4 treatment related toxicity.

The target Grade  $\geq$  3 toxicity rates is no more than 10%, and a toxicity rate greater than 30% is considered clinically unacceptable. The design specified above has the following operating characteristics. The probability of accepting the treatment for further study if the toxicity rate is unacceptably high (> 30%) is at most 10%. In contrast, there is an 80% probability of accepting the treatment for further study if the toxicity rate is less than 10%. In addition, if 0 out of 20 patients experience Grade 4 toxicity at the end of the study, we will be able to conclude with 95% confidence that the true Grade 4 toxicity rate is not greater than 17%.

The proportion of patients who have treatment-related toxicity will be computed, along with exact 95% confidence intervals. Since the study is a phase I trial, we will NOT do any hypothesis testing or models, The study will present the descriptive summary statistics for each outcomes. Biomarker levels measured at different time points and other continuous variables will be summarized by computing means, medians, standard deviations and ranges.

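### The discharge endpoint exists only where there is discharge to swab, so the Week 13 summary cannot show that discharge has stopped

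*Combined protocol and SAP*

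**What the plan says.** Section 1.2 lists as a secondary objective: "To determine possible changes in assessment of cutaneous discharge from HS lesions". Section 4.3 turns this into one measure: "Swabs will be collected from discharge and sent for fluid count, which will include evaluation of infiltrating leukocytes from the discharge". It specifies no presence-or-absence item, volume, drainage score or count of draining lesions. It also does not say which lesion is swabbed, although Section 4.4.2 limits radiotherapy to one region per patient.

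In Section 4.2 the row "Skin Biopsy, Discharge Measurement" is marked at pre-treatment, at Week 13 (within one week either way) and at the optional Weeks 25 and 49. There is therefore one mandatory post-treatment value.

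For analysis, Section 5.0 states: "Biomarker levels measured at different time points and other continuous variables will be summarized by computing means, medians, standard deviations and ranges". It also states: "Since the study is a phase I trial, we will NOT do any hypothesis testing or models". Apart from the pro-rating of unanswered PROMIS items, it gives no rule for values that are missing or cannot be obtained.

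Section 3.1 requires Hurley Stage 2-3 disease, described as "Recurrent abscesses or boils with diffuse or broad involvement, multiple interconnected sinus tracts in the whole area", but does not require active drainage at entry. Section 10.0 names remission as a possible benefit.

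**The concern.** The measurement needs the symptom to be present. A patient whose treated lesions have dried up has the best result this objective could record, yet has nothing to swab. The absence of a value is then caused by the outcome itself, which makes it different from ordinary dropout. A mean or median at Week 13 describes those still draining, and nothing in the defined endpoint registers that discharge has ceased.

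At stake is whether the trial can answer its own secondary question. A cell count in the discharge that remains says what that discharge contains. It does not say how many patients no longer have any.

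**Working it through.** **Inputs**
- Maximum sample size 20 (Section 5.0: "A maximum of 20 patients will be enrolled into the study").
- One mandatory post-treatment discharge assessment, Week 13 (Section 4.2).
- Drying rate d by Week 13: not given. The only figure that bears on it is in Section 2.3: "Complete symptomatic relief was documented in 38% (89/231) patients by the end of therapy". That is 89/231 = 38.5%, used here only as a proxy within a range.
- Assumption: all 20 patients drain at baseline.

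**Step 1: the plan's own figure.** There is none to reproduce. The documents state no effect size, precision or expected number of values for discharge.

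**Step 2: values available at Week 13.** Expected number = 20 × (1 − d).

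**Step 3: what the swab-only summary misses.** Suppose baseline means are equal in those who dry up and those who do not, and counts in patients still draining become k times baseline. The swab-only change is k − 1. With dry scored as zero, the change over all patients is (1 − d)k − 1.

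| d | Week 13 values of 20 | k = 1: swab-only / dry as zero | k = 0.5: swab-only / dry as zero |
|---|---|---|---|
| 10% | 18 | 0% / −10% | −50% / −55% |
| 20% | 16 | 0% / −20% | −50% / −60% |
| 38% | 12.4 | 0% / −38% | −50% / −69% |
| 50% | 10 | 0% / −50% | −50% / −75% |

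**Step 4: does this depend on equal baselines?** Let B be the baseline mean of all patients and M the Week 13 mean among those still draining. The swab-only ratio is M/B; with dry as zero it is (1 − d)M/B, which cannot be larger. Pairing does not change this for relative change. If B₁ is the baseline mean of those still draining, then B ≥ (1 − d)B₁, so (1 − d)M/B ≤ M/B₁.

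**Step 5: direction of the reported mean.** Two invented cases, each with 8 patients drying up and 12 unchanged:
- The 8 start at 60 and the 12 at 125. Baseline mean = (8 × 60 + 12 × 125)/20 = 99; Week 13 mean = 125. The reported mean rises although nobody is worse. With dry as zero, Week 13 = 12 × 125/20 = 75, a 24% fall.
- The 8 start at 160 and the 12 at 60. Baseline mean = (8 × 160 + 12 × 60)/20 = 100; Week 13 mean = 60, a reported 40% fall. With dry as zero, Week 13 = 12 × 60/20 = 36, a 64% fall.

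The reported mean can thus move either way. In both cases it shows less benefit than the all-patient figure.

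**The case against.** The strongest reply is that the plan never says a dry lesion is missing or excluded. A site could enter zero or none, and the calendar row could be read as a wider measurement than a cell count. Section 4.3 also leaves the fluid count undefined and not confined to leukocytes. This stands against any claim to know what will be reported. It does not remove the gap: every count described still comes from a swab of discharge, and nothing tells the site what to record when there is none.

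Physical examination, photographs and the DLQI are collected at every visit, so drying might be recovered from the record. That softens the point, but none of these is designated as a discharge outcome.

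A reader might infer that the trial will report no change or a worse mean, that the two means must come from different patients, or that about 8 of 20 (0.385 × 20 = 7.7) will have no Week 13 swab. The documents support none of these. The mean among those still draining can fall as well as rise, and Section 5.0 neither requires nor rules out paired changes. The 38% is symptomatic relief at the end of therapy across several schedules, not dryness at Week 13. Some patients may not drain at entry, and a swab might be taken outside the treated region.

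A dry visit also proves little alone. Section 2.1 says abscesses may heal within 1-2 weeks, and the case report in Section 2.3 describes recurrences at 3 weeks and 3 months. Without a control arm, natural fluctuation could look like response. This stands and limits how the remedy may be read.

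**Conclusion.** The concern holds in a limited form. As defined, the endpoint cannot register cessation of discharge. If the text is followed literally, the Week 13 summary is conditional on still draining and, relative to scoring dry as zero, understates any benefit. That direction assumes patients drain at baseline; anyone dry at entry who later drains would enter only the Week 13 summary.

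The size is unknown. About 18 to 10 of 20 Week 13 values remain over assumed drying rates of 10% to 50%, with about 12 at the 38% proxy. Scoring dry as zero is only a yardstick here, not a recommended analysis.

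The consequence is confined to one descriptive secondary objective. A reader might take it to threaten the trial's conclusions more widely. It does not: the primary endpoint is safety, and the stopping and acceptance rules in Section 5.0 rest on toxicity alone. The change is still worth making before enrolment, because presence or absence of discharge may not be reliably recoverable later.

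**What to change.** In Section 4.3, record presence or absence of discharge from the treated region at each scheduled physical examination, and treat a dry region with no swab obtainable as an observed result, not as missing.

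In Section 5.0, add:
- the proportion of patients draining at baseline who have no discharge at Week 13, with an exact 95% CI;
- the number dry at baseline who drain at Week 13;
- leukocyte counts as paired changes in patients with discharge at both visits, with that number shown beside the number dry.

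The cost is one field at examinations already scheduled and a few sentences of analysis text, with no added visit or procedure. Two downsides should be stated in the plan. The cell-count result is limited to a subset. The proportion dry is descriptive: without a control arm a single dry visit may reflect natural fluctuation, so it should be read alongside the other visits.

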# 4.4 Radiotherapy

## 4.4.1Immobilization, Simulation, and Localization

Patients will be positioned in a stable position capable of allowing accurate reproducibility of the target position from treatment to treatment. Positions uncomfortable for the patient will be avoided to prevent uncontrolled movement during treatments. A variety of immobilization systems may be used, including stereotactic frames that surround the patient on three sides and large rigid pillows (conforming to patients' external contours) referenced to the stereotactic coordinate system. Patient immobilization will be reliable enough to ensure that

the gross target volume (GTV) does not deviate beyond the confines of the planning treatment volume (PTV) with any significant probability (i.e., < 5%).

# 4.4.2 Target Volumes and Treatment Planning

While patients with hidradenitis suppurativa may have multiple sites of symptomatic disease, subjects on this protocol will only receive radiotherapy directed at one region. This will generally be the region that is most bothersome to the patient.

Computed tomography will be the primary image platform for targeting and treatment planning. Radio-opaque markers may be placed on the patient at the time of simulation to aid with target delineation. Target volumes will be drawn on simulation CT imaging, using appropriate window levels. The general intent will be to include any grossly abnormal areas, based on clinical examination and CT findings, in the GTV. In selected cases of extensive disease, the GTV may be limited to the most problematic area of disease.

The GTV will be expanded to form a PTV. PTV expansions will generally be 10 mm in all directions but may be between 5 and 15 mm depending on the perceived setup uncertainty in each individual case. Nonuniform expansions are permitted, at the discretion of the treating physicians.

Treatment planning will be performed using standard software packages utilized in the Department of Radiation Oncology. Treatment may be delivered using external beam radiotherapy (EBRT) with either photons or electrons, or with high dose rate (HDR) brachytherapy, at the discretion of the treating physicians. The modality that is expected to provide the most complete coverage of the target volumes while minimizing irradiation of uninvolved tissues will generally be selected. The prescription isodose surface should encompass at least 95% of the PTV, and the minimum PTV dose must not fall below 90% of the prescription dose.

Patients in this study will receive a total radiotherapy dose of **7.5 Gy in five daily fractions of 1.5 Gy**.

#### 4.4.3 Critical Structures

The radiotherapy dose used in this protocol is so low that standard dose limits for internal organs will not be exceeded. Nevertheless, careful planning will be utilized to minimize the exposure of all internal organs to radiotherapy. The "as low as reasonably achievable" (ALARA) principle will be employed.

#### 5.0 STATISTICAL CONSIDERATIONS

A maximum of 20 patients will be enrolled into the study. The accrual rate is expected to be 1-2 patients per month based on the volume of patients with stage 2-3 HS treated within the Montefiore Hidradenitis Suppurativa Treatment Center. An early stopping rule for safety will be implemented as follows based on Simon's optimal two-stage design. After the first 6 patients have been enrolled, accrual will be temporarily suspended while these patients are monitored for occurrence of treatment-related grade ≥ 3 toxicity for 3 months. At the end of 3

months, results will be sent to the DSMB for further evaluation. The trial will be terminated early if more than 1 patient experiences grade  $\geq$  3 treatment related toxicity or any patient experiences grade 4 toxicity. Otherwise, upon approval from the DSMB, the second phase of recruiting will be initiated. If 1 or fewer grade  $\geq$  3 toxicities and 0 grade 4 toxicities are observed, the trial will continue until a total of 20 patients have been evaluated. At the end of the trial, the treatment will be considered safe and worthy of further study if no more than 3 patients experience grade  $\geq$  3 treatment related toxicity and none experience grade 4 treatment related toxicity.

The target Grade  $\geq$  3 toxicity rates is no more than 10%, and a toxicity rate greater than 30% is considered clinically unacceptable. The design specified above has the following operating characteristics. The probability of accepting the treatment for further study if the toxicity rate is unacceptably high (> 30%) is at most 10%. In contrast, there is an 80% probability of accepting the treatment for further study if the toxicity rate is less than 10%. In addition, if 0 out of 20 patients experience Grade 4 toxicity at the end of the study, we will be able to conclude with 95% confidence that the true Grade 4 toxicity rate is not greater than 17%.

The proportion of patients who have treatment-related toxicity will be computed, along with exact 95% confidence intervals. Since the study is a phase I trial, we will NOT do any hypothesis testing or models, The study will present the descriptive summary statistics for each outcomes. Biomarker levels measured at different time points and other continuous variables will be summarized by computing means, medians, standard deviations and ranges.

PROMIS scores will be calculated using "PROMIS scoring manuals" found at http://www.healthmeasures.net/promis-scoring-manuals. The formula for scoring is: (Raw Sum of all questions answered X number of items on the short form) / Number of items that were actually answered. Using the provided score conversion table, the pro-rated raw score will be converted into a T-score for each participant.

Interpretation of PROMIS scores will be completed as explained at http://www.healthmeasures.net/score-and-interpret/interpret-scores/promis. T scores for each participant will be compared to calibrated scores of a validated reference population, where a score of 50 is the average for the United States general population with a standard deviation of 10.

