## 4.0 STUDY DESIGN

# 4.1 General Design

• This phase I clinical trial will use a Simon two-stage design. In the first stage, 6 patients will be enrolled, if the patients in the study do not meet the termination criteria then the study will extend to a second stage and we will enroll a maximum of 20 patients. Patients will be treated with skindirected radiotherapy, using a total prescription dose of 7.5 Gy in five fractions of 1.5 Gy over one week. Neither patient nor insurance will be billed for the radiotherapy procedures. If any subject experiences Grade > 3 toxicities, the study will be stopped and the IRB will be informed immediately so the study can be reevaluated.

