#### Interim Analysis.

Once the first 6 patients are recruited, the study recruitment will be temporarily suspended and the patients will be followed for 3 months to monitor any toxicity issues. At the end of 3 months follow-up of the 6 patients, the results will be sent to the DSMB for further evaluation. The trial will be terminated if grade 3 or more toxicity is observed in more than 2 patients or at least one showing grade 4 level toxicity. Otherwise, upon approval from the DSMB, the second phase of recruiting will be initiated.

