# 8.0 Data Safety and Monitoring Boards

A Data Safety Monitoring Committee is being convened by [name]. They will have the responsibility for ensuring data and safety monitoring along with the PI who is ultimately responsible for the ongoing monitoring and safety of clinical protocols. The primary functions of this DSMC are as follows:

- To review and ensure protocol compliance with dose escalation in phase I trials
- 2. To review/assure protocol compliance for all trials that have two-stage phase II designs,
- Reviewing all internal and external serious adverse reports, investigator alerts, action letters, and other safety reports for trials being performed at AECC-affiliated institutions and;
- 4. To implement and to determine the adequacy of DSM plans of all approved protocols.

The committee will meet quarterly or more frequently as needed. This committee lead by [name] will review serious (grade 3 or higher) adverse events from this study. In the event that the DSMC decides that a revision is warranted, the committee will immediately notify the principal investigator of this study. The DSMC has the authority to close trials to patient accrual should the risk to patients be excessive or outweigh the potential benefits of the study. All study

suspensions and closures will be forwarded to the IRB/CCI and study sponsor from the DSMC.

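### The stage 1 toxicity boundary is written as a check after the 3-month review, so two early Grade 3 events do not automatically stop enrolment of the remaining stage 1 patients

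*Combined protocol and SAP*

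**What the plan says.** Section 5.0 sets out stage 1 as a sequence. "After the first 6 patients have been enrolled, accrual will be temporarily suspended while these patients are monitored for occurrence of treatment-related grade" 3 or higher toxicity over 3 months. The results are then sent to the DSMB. The boundary follows: "The trial will be terminated early if more than 1 patient experiences grade" 3 or higher treatment-related toxicity, or if any patient has Grade 4. The boundary sentence carries no date of its own.

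The Interim Analysis text in section 4.1 uses the same order: "At the end of 3 months follow-up of the 6 patients, the results will be sent to the DSMB for further evaluation". Its count comes next and differs from 5.0: "The trial will be terminated if grade 3 or more toxicity is observed in more than 2 patients".

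One rule is written as immediate, also in 4.1: "If any subject experiences Grade > 3 toxicities, the study will be stopped and the IRB will be informed immediately". As printed, it does not cover Grade 3.

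On timing, section 5.0 says "The accrual rate is expected to be 1-2 patients per month", and the row "Adverse Event Assessment" of the study calendar (4.2) is marked at Weeks 1, 5, 9 and 13. No minimum interval between the first six patients is given.

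Section 8.0 has the DSMC review Grade 3 or higher events, meet at least quarterly and hold power to close accrual, "along with the PI who is ultimately responsible for the ongoing monitoring and safety of clinical protocols".

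**The concern.** Under the 5.0 rule, a second patient with Grade 3 or higher treatment-related toxicity fixes the stage 1 outcome, and no later stage 1 patient can reverse it. Followed in its printed order, the plan still completes enrolment of six and waits 3 months before the count is applied. Because accrual is slow relative to the visit schedule, two early events can be known while later stage 1 patients are still entering. Pausing at that point depends on PI and DSMC judgement, and section 8.0 ties neither to the 5.0 count.

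The exposure is bounded. Accrual is already suspended from the sixth enrolment until DSMB approval, and a single Grade 4 event already stops the study. Only Grade 3 events, and only patients 3 to 6, are in question. Those patients would be irradiated for a benign disease without being able to change the stage 1 decision.

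**Working it through.** **Inputs.** From 5.0: stage 1 of 6 patients, stop if more than 1 has toxicity; total 20, accept if no more than 3 do; toxicity rates 10% (target) and 30% (unacceptable); accrual 1 to 2 per month. From 4.2: visits at Weeks 1, 5, 9 and 13. Not in the documents, so assumed: time to onset, reporting delay, evenly spaced enrolment, and radiotherapy starting at enrolment.

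**Step 1: the plan's own figures.** Leaving aside the separate Grade 4 rule,

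P(accept) = Σ over x = 0, 1 of P(Bin(6, p) = x) × P(Bin(14, p) ≤ 3 − x).

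This gives 0.806 at p = 0.10 and 0.090 at p = 0.30, in line with the stated 80% and at most 10%. With the 4.1 count (stop only if more than 2), x runs to 2 and the values are 0.864 and 0.106.

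**Step 2: effect of acting at the second event.** Acceptance requires at most one event in stage 1. Suspending at the second event touches only trials that 5.0 would terminate anyway, so 0.806 and 0.090 do not change.

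**Step 3: worked example.** The sixth patient enters five intervals after the first: month 5 at 1 per month, month 2.5 at 2 per month. Suppose patients 1 and 2 both have Grade 3 toxicity, with patient 2 enrolled at month 1.0 or 0.5.

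- Recorded at Week 5 (about 1.15 months after enrolment): known at month 2.15 or 1.65. Patients 4 to 6 (three) or 5 to 6 (two) are still to enter.
- Recorded at Week 1 (about 0.23 months): known at month 1.23 or 0.73. Patients 3 to 6 (four) are still to enter at either rate.

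A Week 5 visit held one week early, as 4.2 allows, changes three and two to four and three.

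**Step 4: ceiling with no effective lag.** At least one patient enters after the boundary is met if two or more of the first five have events: P(Bin(5, p) ≥ 2) = 0.472 at 30%, 0.081 at 10%, and 0.004 at an assumed 2%. The expected number of such patients at 30% is Σ over k = 2 to 5 of P(Bin(k, 0.3) ≥ 2) = 0.090 + 0.216 + 0.348 + 0.472 = 1.13.

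**Step 5: allowing for lag.** Simulation, 400,000 trials per setting, p = 0.30, onset uniform over the stated window, with neither PI nor DSMC acting early. Entries are the chance that at least one stage 1 patient is enrolled after the second event is known.

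| Events known | Onset window (months) | Reporting delay (months) | 1 per month | 2 per month |
|---|---|---|---|---|
| Next scheduled visit | 0–1 | 0 | 37.7% | 27.6% |
| Next scheduled visit | 0–1 | 0.5 | 37.7% | 14.8% |
| Next scheduled visit | 0–3 | 0 | 27.6% | 7.1% |
| Next scheduled visit | 0–3 | 0.5 | 23.7% | 2.3% |
| At onset | 0–1 | 0 | 47.2% | 41.1% |
| At onset | 0–1 | 0.5 | 41.1% | 28.4% |
| At onset | 0–3 | 0 | 34.6% | 16.1% |
| At onset | 0–3 | 0.5 | 28.2% | 7.6% |

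Mean patients enrolled after the boundary: 0.03 to 0.76 (visits only) and 0.11 to 1.13 (at onset).

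**Step 6: sensitivity.**

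- At the 10% target: 0.3% to 6% (visits only) and 0.9% to 8% (at onset).
- At 30%, if 20% of the events are Grade 4 and already stop the study (assumption): 1.5% to 24% and 5% to 30%.
- At 30%, with a 1-month reporting delay: 0.6% to 24.7% and 2.6% to 34.8%.
- At 30%, using the 4.1 boundary (third event): 0.1% to 10.3% and 0.6% to 16.3%.

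**The case against.** The strongest reply is that 5.0 presents this as an early stopping rule and puts no time limit on the termination sentence, so it can be read as applying at any time. That stands as a possible reading. The defect is ambiguity, not a stated delay, but a stopping rule should not depend on which reading the site adopts.

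Second, if the sign in the 4.1 immediate stop was meant to include Grade 3, one such event would already pause the study and the gap would close. This cannot be settled from the documents. The separate Grade 4 clauses in 4.1 and 5.0 fit the sign as printed, though they do not prove it.

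Third, other safeguards exist. The DSMC's listed functions include compliance with two-stage phase II designs, section 6.2 lets the PI deviate to remove an immediate hazard, and the Reportable Events Policy may add more. The first two do not make the count act early. The policy is not in the documents, so its effect cannot be judged.

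Fourth, the upper figures need toxicity at the unacceptable bound, inaction by both PI and DSMC, and assumed lags. That is correct. Section 2.3 reports no acute side effects in 231 patients, at varied doses. Zero of 231 has a one-sided 95% upper bound of 1 − 0.05^(1/231) = 1.3%, where the ceiling in Step 4 is about 0.2%. Section 10.0 also calls the dermatitis risk very low.

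Last, applying a Simon boundary at the end of stage 1 is the standard form of the design. That is why this is an improvement to a design choice, not the correction of an error.

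**Conclusion.** The concern holds on the text as printed. Section 5.0 does not say that its stage 1 boundary acts once reached, and for Grade 3 events the plan contains no automatic pause before patients 3 to 6. At most four patients are affected. At 30% toxicity the chance that at least one is enrolled after the boundary is met is 2% to 47%, with a mean of 0.03 to 1.1 patients; at 10% it is 0.3% to 8%. These figures assume no early action by the PI or DSMC, and onset and reporting lags that the plan does not give. The benefit is modest, and very small if toxicity is as rare as section 2.3 suggests. The change is still worth making because it protects patients directly and leaves the error rates as they are.

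**What to change.** Add to 5.0, and to 4.1 once its count is aligned with 5.0:

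> The stage 1 boundary applies as soon as it is reached. If a second patient has Grade ≥3 treatment-related toxicity, enrolment and the start of radiotherapy in further patients are suspended at once, and the data are sent to the DSMB without waiting for the 3-month look.

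The 4.1 count (more than 2) has to be changed to more than 1 first, because the two sections otherwise trigger at different events. The authors should also confirm whether the immediate stop in 4.1 is meant to cover Grade 3. If it is, correcting the sign there closes the gap.

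The cost is one sentence in each section, using the existing boundary and committee. The maximum sample size and the acceptance probabilities do not change. The one downside is a less precise toxicity estimate in a trial that would be terminated anyway.
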